4.3. CONCOMITANT EVENTS

It is expected that during the development of the study the events defined in this section will take place. The aim of this section is to define flags that will be created in the datasets and that will guide the analysis of the endpoints as defined in Section 4.7.

4.3.1. Start of symptomatic PD treatment

The start of symptomatic PD treatment visit will be derived according to the following algorithm:

1. For patients who are treatment naïve at baseline, symptomatic PD treatment includes the following medications: COMT inhibitors [entacapone, tolcapone], amantadine or anticholinergics, dopamine medication [levodopa], both ergot and non-ergot (pramipexole, ropinirole, rotigotine) treatments, MAOB inhibitors [rasagiline, selegine, safinamide], and dopamine agonists. These medications received by the patient during Part 1 will be extracted from the Concomitant Medications SDTMv domain (from Targeted ConMed eCRF page). The symptomatic PD treatments will be selected with the following criteria from the WHODrug dictionary: ATC Class Level 2 should be equal to "ANTI-PARKINSON DRUGS" (Class code N04).

For patients on MAOB inhibitors at baseline, symptomatic PD treatment is defined as COMT inhibitors [entacapone, tolcapone], amantadine or anticholinergics, dopamine medication [levodopa], both ergot and non-ergot (pramipexole, ropinirole, rotigotine) treatments, and dopamine agonists received by the patient during Part 1. In addition, also an increase in dose or regimen of the MAO-B inhibitors compared to baseline is considered as "symptomatic PD treatment". MAOB inhibitors will be selected from the concomitant medications at baseline when ATC Class Level 4 is equal to "MONOAMINE OXIDASE B INHIBITORS" and their dose/regimen increases when compared to baseline

2. The date when the first symptomatic PD treatment was received or an increase in dose/regimen in MAOB inhibitor from baseline happened (whichever is first) will be marked as the "first symptomatic PD treatment date".
3. All visits with a date after the date of the first intake of symptomatic PD treatment will be flagged and considered as "after first symptomatic PD treatment".

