#### **4.5.1 Permitted Therapy**

##### **4.5.1.1 For Participants on MAO-B Inhibitor Therapy**

Participants who are currently under treatment for PD with a MAO-B inhibitor (rasagiline or selegiline), should be on a stable dose for at least 90 days prior to baseline and during the first year of the study (prior to extension). These patients will be treated with stable daily doses as recommended by the USPI or SmPC for rasagiline monotherapy and selegiline monotherapy and should not increase doses or switch between different MAO-B inhibitors during the study. Furthermore, if a participant is on a stable and well tolerated treatment regimen of a combination of a selective MAO-B inhibitor (rasagiline or selegiline) and an antidepressant for a period of at least 6 months prior to baseline, he/she may, at the discretion of the treating physician and in accordance with the local standard of care, continue on this therapy (without increasing the dosage) for the duration of their participation in the study.

Participants that are untreated at baseline should not start MAO-B inhibitor treatment during the 52-week placebo controlled period (Part 1). If participants do start MAO-B inhibitor treatment at any time during the study, they will also complete the assessments described in the SoA under “prior to start of dopaminergic/symptomatic PD treatment”. Likewise, any changes of MAO-B inhibitor treatment and the reasons will be recorded.

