### **6.6.1 Primary Efficacy Endpoint**

The primary efficacy endpoint is the change in total MDS-UPDRS (sum of Parts I, II and III) from baseline to Week 52 (end of Part 1 of the study).

The primary efficacy endpoint will be analyzed using a MMRM with the covariates described in Section 6.6 and visit (seven levels) as fixed effects, treatment-by-visit interaction term, and the baseline value for total MDS-UPDRS (sum of Parts I, II and III) as a covariate; an interaction term between baseline MDS-UPDRS by visit will also be included. Within each participant, the model will incorporate an unstructured variance-covariance matrix for the random error terms. Observations from different participants are considered independent. For each active dose arm tested at the final analysis, this model will be used to test the null hypothesis of no treatment difference between the placebo arm and each active arm at a two-sided  $\alpha$ -level of 20%, which corresponds to a one-sided  $\alpha$ -level of 10%.

Starting symptomatic PD treatment for the statistical analysis is defined as starting COMT inhibitors (entacapone, tolcapone), amantadine, anticholinergics, levodopa, dopamine agonists, or MAOB inhibitors and - for patients already on MAO-B inhibitors at baseline - also increases in dose or regimen of the MAOB inhibitor. Assessments performed after starting symptomatic PD treatment will not be included in the primary analysis.

Missing values will be handled via the MMRM methodology.

The primary endpoint will also be summarized using descriptive statistics.

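### For patients on an MAO-B inhibitor at baseline, SAP 4.3.1 gives no clear rule for flagging a different MAO-B inhibitor started during Part 1

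*SAP*

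**What the plan says.** SAP 4.3.1 builds the flag that ends a participant's contribution to the primary MMRM, and it uses two lists. For patients untreated at baseline, the list includes "MAOB inhibitors [rasagiline, selegine, safinamide], and dopamine agonists". For the others it begins "For patients on MAOB inhibitors at baseline, symptomatic PD treatment is defined as COMT inhibitors [entacapone, tolcapone], amantadine or anticholinergics, dopamine medication [levodopa" and continues without any MAO-B inhibitor.

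For these baseline users a further trigger follows: "In addition, also an increase in dose or regimen of the MAO-B inhibitors compared to baseline is considered as" symptomatic treatment. The section then says how the trigger is found: "MAOB inhibitors will be selected from the concomitant medications at baseline when ATC Class Level 4 is equal to" the MAO-B class, "and their dose/regimen increases when compared to baseline".

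Protocol 6.6.1 has one list for everyone. Starting any of its drugs counts, and the list ends with "levodopa, dopamine agonists, or MAOB inhibitors and - for patients already on MAO-B inhibitors at baseline - also increases in dose or regimen". The SAP's Background section states that the SAP replaces the protocol's analysis plan, so where the two differ the SAP governs.

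Protocol 4.5.1.1 treats a switch as something distinct from a dose increase. Participants "should not increase doses or switch between different MAO-B inhibitors during the study", and "any changes of MAO-B inhibitor treatment and the reasons will be recorded".

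**The concern.** A baseline user who adds a second MAO-B inhibitor, or exchanges one for another, has begun a new symptomatic drug. Under the SAP that drug is not on the user's list. It is also not among the medications selected at baseline, so the dose-or-regimen check does not literally reach it. If a programmer makes the comparison anyway, a switch sets amounts of two different drugs against each other with no conversion given, and the flag then depends on units.

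The estimand in SAP 4.7.2 asks what would have happened had symptomatic treatment not been started. Scores taken under an unflagged new agent would enter the model as if that condition held. The same handling applies to the MDS-UPDRS part scores, CGI-I and PGIC (SAP 4.7.3). Without a written rule, the choice falls to case-by-case programming on the primary endpoint.

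**Working it through.** **Text comparison.** The cases, read literally:

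| Change in Part 1 | Protocol 6.6.1 | SAP 4.3.1 |
|---|---|---|
| Untreated patient starts an MAO-B inhibitor | counts | counts |
| User increases the same drug | counts | counts |
| User adds a second MAO-B inhibitor | counts as a start | not listed; counts only if read as a regimen increase |
| User switches to another MAO-B inhibitor | counts as a start | not listed; no dose scale for comparison |
| User stops or reduces | does not count | does not count |

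The documents part company only in the third and fourth rows. SAP 4.10 excludes assessments made on symptomatic treatment begun after randomization, or after such treatment is increased. It relies on the term that 4.3.1 defines, and for baseline users that definition leaves MAO-B drugs out. So 4.10 does not settle these two rows.

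**The plan's own power figure.** SAP 2.4 gives 100 per arm, a 3-point difference, SD 9 at Week 52, 25% (placebo) and 20% (active) non-evaluable, correlation 0.55 and two-sided alpha 20%. It states power of about 80%.

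- Week 52 completers only: SE = 9 × √(1/75 + 1/80) = 1.447; power = Φ(3/1.447 − 1.2816) = 78.6%.
- MMRM information with the Table 1 SDs and missingness: SE = 1.374; power = Φ(3/1.374 − 1.2816) = 81.6%.

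Both agree with the stated figure. The MMRM standard error serves as the yardstick below.

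**Size of the gap.** The documents give no share of MAO-B users, no rate of new agents and no score shift, so all three are assumptions.

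Bias in the treatment difference = share of users × between-arm difference in the rate of unflagged new agents × score shift.

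- Moderate case: 35 users per 100, all changes in one arm at 3% to 10% of users, shift 3 points. Patients affected: 35 × 0.03 = 1.05 to 35 × 0.10 = 3.5. Bias: 0.35 × 0.03 × 3 = 0.03 to 0.35 × 0.10 × 3 = 0.105 point, which is 1% to 3.5% of the 3-point effect and 0.02 to 0.08 standard errors. If it works against the drug, power is Φ(2.9685/1.374 − 1.2816) = 81.0% to Φ(2.895/1.374 − 1.2816) = 79.5%.
- Wide case: share 20% to 50%, rate difference 5 to 20 percentage points, shift 2 to 4 points. Bias: 0.20 × 0.05 × 2 = 0.02 to 0.50 × 0.20 × 4 = 0.40 point, or 0.7% to 13%. At the extreme, power is 72.9% if the bias works against the drug, and the two-sided error under the null is 21.9% instead of 20%.
- Equal rates in both arms: bias near zero.

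The sign depends on which arm has more changes. If an added drug lowers scores, an excess on placebo hides benefit and an excess on active treatment imitates it.

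**The case against.** **Regimen, not dose alone.** The trigger covers regimen as well as dose, and the step in 4.3.1 that sets the date speaks of the MAO-B class. An added second agent can fairly be read as a regimen increase. This stands, and a reader who infers that the SAP looks only for a dose increase, or that every added agent escapes, goes further than the text allows. It does not help with a one-for-one switch.

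**The protocol may mean the same thing.** Protocol 6.6.1 could be taken as starts for untreated patients and increases for users. Protocol 6.6.2 gives this some support, because it speaks of data after symptomatic treatment or after an increase in MAO-B therapy. The plainer reading is that the increases are added to a rule covering everyone. On either reading, the SAP does not say what happens to a new agent.

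**Rarity.** Protocol 4.5.2.1 bars other selective MAO-B inhibitors for participants already on one, inclusion criterion 7 requires a stable dose not expected to change within 52 weeks, and SAP 4.4.3 summarizes major deviations by arm. This stands and is the main reason the effect should be very small. A deviation table does not, however, remove scores from the model.

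**Stopping or reducing.** A reader might also infer that the rule is wrongly one-sided, because scores after the background drug is stopped or reduced are kept. The documents do not support calling that an error. Neither lists it as an event that ends data, and the estimand concerns the start of symptomatic treatment, so keeping those scores is consistent with it.

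**Like-for-like switches.** Counting every switch as a start discards some scores where treatment did not escalate. This is a real cost of the fix, though a small one.

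**Conclusion.** The gap is real and narrow. For baseline users, SAP 4.3.1 as written does not reliably flag an MAO-B inhibitor first taken in Part 1. It is narrower there than the plain reading of Protocol 6.6.1, and SAP 4.10 does not close the difference.

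The expected effect on the primary result is very small: about 0.03 to 0.1 point under moderate assumptions, and near zero with balanced changes. The 0.40-point figure needs half of the patients on MAO-B inhibitors, a 20-point imbalance and a 4-point shift together, which is hard to square with the protocol's restrictions. The moderate rates are themselves generous, since they place every change in one arm. A reader should not infer that the primary comparison is materially biased; nothing in the documents shows that. The reason to act is that a primary-endpoint flag should not be left to interpretation when the correction costs almost nothing.

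**What to change.** In the second paragraph of item 1 in SAP 4.3.1, state for the analysis flag that starting any MAO-B inhibitor not taken at baseline, whether added or substituted, counts as the start of symptomatic PD treatment. Extend the medication selection to Part 1 records accordingly, and limit the dose and regimen comparison to the same drug. Align SAP 4.10 by pointing it to this definition. Report the number of such changes by arm, for example with the patient disposition tables in SAP 4.4.4.

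As an option, add one run of the primary MMRM that also ends data when the baseline MAO-B inhibitor is stopped or reduced.

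The cost is a few lines of text and one count. The protocol already requires MAO-B changes and their reasons to be recorded, so no new data are needed, and no participant's treatment is affected. The downside is a few more excluded visits, some of them after like-for-like switches.

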4.3.2. Start of dopaminergic treatment

The start of dopaminergic treatment visit will be derived according to the following algorithm:

1. All the dopaminergic treatments defined as dopamine medication [levodopa], both ergot and non-ergot (pramipexole, ropinirole, rotigotine) treatments and dopamine agonists received by the patient during Part 1 will be extracted from

the Concomitant Medications SDTMv domain (from Targeted ConMed eCRF page). The dopaminergic treatments will be selected with the following criteria from the WHODrug dictionary: ATC Class Level 4 should be equal to " DOPA AND DOPA DERIVATIVES or DOPAMINE AGONISTS".

2. The date when the first dopaminergic treatment was received will be marked as the "first dopaminergic treatment date".
3. All visits with a date after the date of the first intake of dopaminergic treatment will be flagged and considered as "after first dopaminergic treatment".

4.3.3. Defined symptomatic treatment start

The last visit whose date is before or the same date of the "first symptomatic PD treatment date" (as described in Section 4.3.1) will be flagged as the "Defined symptomatic treatment start".

4.3.4. Defined dopaminergic treatment start

The last visit whose date is before or the same date of the "first dopaminergic treatment date" (as described in Section 4.3.2) will be flagged as the "Defined dopaminergic treatment start".

4.3.5. Practically defined "Off" state

Participants who have started dopaminergic PD treatment (as per Section 4.3.2) during the course of the study will continue in the study, as per their regular scheduled study visits. For these participants, the MDS-UPDRS (Parts I, II, III and IV) will be performed in a practically defined "Off" state – no levodopa or dopamine agonist medication since the prior evening, and Part III (motor assessment) will be repeated at least one hour after receiving medication in clinic ("On" state).

For MDS-UPDRS Part III collected on the same visit day, the earliest date/time stamp will indicate that the measurement was undertaken during the OFF state. The second measurement will be flagged as the ON state.

For participants who have started symptomatic PD treatment different from dopa or dopamine agonists, the MDS-UPDRS Part III will not be repeated in "OFF" and "ON" state due to the long half-life of these compounds. If only one MDS-UPDRS Part III is collected on the visit date after starting symptomatic PD treatment different from dopa or dopamine agonists, this will be labelled as Practically defined "OFF" state. If two MDS-UPDRS Part III are collected on the same visit day, the earliest date/time stamp will be included as Practically defined "OFF" state.

4.4. ANALYSIS OF STUDY CONDUCT

4.4.1. Screening

The number of patients who were screened and the number and percentage of patients who were screen failures will be reported.

4.4.2. Study enrollment

The number of patients randomized will be summarized by treatment group, country, and study site.

4.4.3. Protocol Deviations

Protocol deviations will be reviewed and reported in accordance with the 'Global: Protocol Deviations' standard operating procedure (SOP-0105983). Major protocol deviations will be identified according to the Protocol Deviation Management System (PDMS) before data cut. The number and percentage of patients with major protocol deviation will be summarized by treatment group and protocol deviation category (inclusion criteria, exclusion criteria, procedures, or medication) and by inclusion/exclusion criteria not met.

4.4.4. Patient Disposition

Patient disposition (the number and percentage of patients randomized, receiving at least one dose of study drug during the treatment period, randomized but not receiving study drug, completed Part 1, discontinued from study, and time on study) will be summarized by treatment arm. Reasons for premature withdrawal from study will be summarized by treatment group.

The number and percentage of patients who started symptomatic PD treatment (as described in Sections 4.3.1) will be reported by treatment group, visit and country.

4.5. ANALYSIS OF TREATMENT GROUP COMPARABILITY

Demographics and baseline characteristics, including, but not limited to age, sex, race, ethnicity, weight, height, BMI, Hoehn & Yahr and modified Hoehn & Yahr (mH&Y) scale, MoCA, total (sum of Parts I, II, and III) and Part I, II and III of MDS-UPDRS, PDQ-39, SE-ADL, DaT-SPECT striatum, putamen and caudate (ipsilateral, contralateral and average) , MAOB inhibitor treatment (Yes/No), RBDSQ Multi Item (< 5 , ≥ 5), MDS-UPDRS sub-scores: Parts IA, Part IB, Part I total and II, Parts III, and Part III subscores, PDSS-2, SCOPA-AUT, skin biopsy (positive or negative), mean diffusivity (MD) MRI, fractional anisotropy (FA) MRI, and cerebral blood flow (CBF) MRI striatum, putamen and caudate (ipsilateral, contralateral and average) will be summarized for the mITT population by treatment arm with the use of descriptive statistics.

4.6. TIME WINDOWS

The analysis of data will be undertaken using time windows. As all the endpoints in the study are collected at different time frequencies, three different set of time windows will be applied depending on the endpoint. The analysis of all the endpoints collected every four weeks will be undertaken using the time windows described in Table 3. For the scales and questionnaires collected every eight weeks or more, Modified Hoehn & Yahr, MDS-UPDRS, CGI-I, PGI-C, MoCA, PDQ-39, SCOPA-AUT, SE-ADL, and PDSS-2, the time windows that will be used in the analysis are described in Table 4. All the endpoints collected with the remote device will be analysed with the windows described in Table 5.

The reporting windows will be applied to every single data point obtained for analyses regardless of the visit label used to collect the data, i.e. scheduled, unscheduled, or prior to start symptomatic treatment visits. If there are two or more visits mapped to exactly the same reporting window, then the following rules will be used to apply the data analysis flag to the assessment, i.e. the data flag used for the by visits reported as described in this SAP:

1. If neither of the visits are labelled as “Prior to start dopaminergic treatment visit” (as per protocol), flag the data from the last available visit.
2. If any visit is labelled as “Prior to start dopaminergic treatment visit” (as per protocol), then flag the data from this visit in the analysis.

Table 3. Windows for assessments collected every four weeks (vitals, physical examination, C-SSRS, ECG, ADAs, hematology, etc).

	Scheduled Week	Scheduled Day	Reporting window		
Part 1	1	1	≤ 1		
	1	2	2	to	4
	1	7	5	to	10
	2	14	11	to	20
	4	28	21	to	41
	8	56	42	to	69
	12	84	70	to	97
	16	112	98	to	125
	20	140	126	to	153
	24	168	154	to	181
	28	196	182	to	209
	32	224	210	to	237
	36	252	238	to	265
	40	280	266	to	293
	44	308	294	to	321
48	336	322	to	349	
52	364	350	to	Day before re-randomization to Part 2	

Table 4. Windows for assessments collected every 8 weeks or more

	Scheduled Week	Scheduled Day	Reporting window		
Part 1	1	1	≤ 1		
	8	56	2	to	83
	16	112	84	to	139
	24	168	140	to	195
	32	224	196	to	251
	40	280	252	to	307
	48	336	308	to	349
	52	364	350	to	Day before re-randomization to Part 2

Table 5. Windows for assessments collected in the remote device

	Scheduled Week	Scheduled Day	Reporting window		
Part 1	1	1	≤ 1		
	2	14	2	to	20
	4	28	21	to	34
	6	42	35	to	48
	8	56	49	to	62
	10	70	63	to	76
	12	84	77	to	90
	14	98	91	to	104
	16	112	105	to	118
	18	126	119	to	132
	20	140	133	to	146
	22	154	147	to	160
	24	168	161	to	174
	26	182	175	to	188
	28	196	189	to	202
	30	210	203	to	216
	32	224	217	to	230
	34	238	231	to	244
	36	252	245	to	258
	38	266	259	to	272
	40	280	273	to	286
	42	294	287	to	300
	44	308	301	to	314
	46	322	315	to	328
48	336	329	to	342	
50	350	343	to	356	
52	364	357	to	Day before re-randomization to Part 2	

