#### **4.6.1.3 Vital Signs**

Vital signs will include measurements of temperature, respiratory rate, pulse rate, and systolic and diastolic blood pressure while the patient is in a semi-supine position (upper body is not completely horizontal but rather tilted at an angle of about 45°) after the patient has been resting for approximately 5 minutes at each visit. Additionally, a single BP and pulse will be obtained after 2 minutes of standing for orthostatic vital signs at the time-points specified in the SoA ([Appendix 1](#), [Appendix 2](#) and [Appendix 3](#)). When possible, the same arm should be used for all blood pressure measurements.

*In Part 1 and 2, blood pressure (BP), pulse rate, respiratory rate and body temperature will be recorded at the time-points specified in the SoA ([Appendix 1](#) and [Appendix 2](#)). In Part 3, blood pressure (BP), pulse rate and respiratory rate will be recorded at the time-points specified in the SoA; body temperature may be taken at any visit if deemed necessary by the Investigator but is no longer mandatory at each visit ([Appendix 3](#)).*

Any clinically significant abnormal vital sign value should be repeated to ensure accuracy. If the abnormality persists upon repeat measurement, the patient should be assessed by the Investigator.

Blood pressure, pulse rate and respiratory rate should be obtained in a quiet room at a comfortable temperature, with the participant's arm unconstrained by clothing or other material. All measurements will be obtained from the same arm and, with the same cuff size, using a well-calibrated automatic instrument with a digital readout, throughout the study (the "ideal" cuff should have a bladder length that is 80% and a width that is at least 40% of arm circumference [a length-to-width ratio of 2:1]). The automatic cuff should be placed on the designated arm prior to dosing. The participant should be asked to remove all clothing that covers the location of cuff placement. The individual should be comfortably seated, with the legs uncrossed, and the back and arm supported, such that the middle of the cuff on the upper arm is at the level of the right atrium (the mid-point of the sternum). After the patient has been resting in a semi-supine position for at least 5 minutes, blood pressure, pulse rate and respiratory rate will be obtained.

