#### **4.6.1.5 Laboratory Assessments**

Normal ranges for the study laboratory parameters must be supplied to the Sponsor before the study starts. Laboratory safety tests shall be collected at time-points specified in the SoA ([Appendix 1](#), [Appendix 2](#) and [Appendix 3](#)).

Additional blood or urine samples may be taken at the discretion of the Investigator if the results of any test fall outside the reference ranges, or clinical symptoms necessitate additional testing to monitor participant safety. Where the clinical significance of abnormal lab results is considered uncertain, screening lab tests may be repeated once per discretion of the Investigator before randomization to confirm eligibility. If there is an alternative explanation for a positive urine or blood test for drugs of abuse, e.g., previous occasional intake of a medication or food containing for example codeine, benzodiazepines or opiates, the test could be repeated to confirm washout.

After randomization, in the event of unexplained abnormal clinically significant laboratory test values, the tests should be repeated immediately and followed up until they have returned to the normal range and/or an adequate explanation of the abnormality is found. Results from local or central clinical laboratory testing will be either recorded on the eCRF or be received as electronically produced laboratory reports submitted directly from the central laboratory and loaded on the eCRF.

Blood and urine samples will be collected for the following clinical laboratory tests at the time-points indicated in the SoAs ([Appendix 1](#), [Appendix 2](#) and [Appendix 3](#)).

- Hematology (leukocytes, erythrocytes, hemoglobin, hematocrit, platelets, differential count [neutrophils, eosinophils, basophils, monocytes, lymphocytes, other cells]).
- Serum chemistry (sodium, potassium, chloride, bicarbonate, glucose (fasting for screening visit), urea, creatinine, protein, albumin, phosphate, calcium, total and direct bilirubin, alkaline phosphatase, ALT, AST, urate, LDH).
- Coagulation (INR, aPTT, PT)
- Viral serology:
  - HIV (specific tests HIV-1 antibody, HIV-1/2 antibody, HIV-2 antibody)
  - Hepatitis B surface antigen (HBsAg)
  - Total hepatitis B core antibody (HBcAb)
  - Hepatitis C virus (HCV) antibody
  - HCV RNA test for successfully treated HCV patients

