4.9.2. Adverse Events

Verbatim descriptions of treatment-emergent adverse events will be coded using the latest version of MedDRA in effect at the time of database freeze. A treatment-emergent adverse event is defined as any new adverse event or any worsening of an existing condition with an onset date on or after the first study drug administration date.

Summaries of treatment-emergent events will be provided for each of the following categories:

- Incidence of adverse events
- Incidence of adverse events by intensity
- Incidence of adverse events by relationship to study medication
- Incidence of serious adverse events
- Incidence of adverse events leading to discontinuation of study treatment
- Incidence of adverse events of special interest
- Incidence of infusion related reactions

- C-SSR will be reported by visit

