4.9.5. ECG Data Analysis

ECG data will be presented by individual listings (each individual triplicate result will be listed) with flagging of values outside the normal ranges (Table 8) and flagging of marked abnormalities. If the overall interpretation for an ECG is normal, specific flagged abnormalities will not be listed. ECG results with a technical quality abnormal finding will be listed.

In addition, tabular summaries will be used, as appropriate. Incidence of ECG abnormalities (including changes from baseline) will be reported. The relationship between QTcF prolongation and the serum concentration of prasinezumab may be investigated in an exploratory manner. If positive dose-response trends are observed with prasinezumab in these analyses, concentration-QT modeling may be conducted with data pooled across studies PRX002-CL002 and BP39529.

The number and percentage of subjects falling into the clinical signal categories for QT/QTc (≤ 450 , $450 <$ and ≤ 480 , $480 <$ and ≤ 500 , $500 <$) will be provided by treatment and time-point. Sex or age specific drug effects on QT are possible and will be investigated.

RR measurements on selected safety ECGs (i.e. Baseline/Day 1 (pre-dose), Week 52 and Week 104, or early termination), will be provided by Biotelemetry for an exploratory Heart Rate variability analysis. The standard deviation of the RR interval for the individual participant may be assessed as an exploratory endpoint.

Table 8. ECG normal ranges

Parameters	Method	Low	High
Heart Rate ECG (bpm)	12 LEAD TRIPLICATE	50	99
PQ(PR) (msec)	12 LEAD TRIPLICATE	110	200
QRS (msec)	12 LEAD TRIPLICATE	80	100
Mean RR interval (msec)	12 LEAD TRIPLICATE	926 (range 785-1160)	
SDNN (standard deviation of normal-to-normal intervals) (msec)	12 LEAD TRIPLICATE	50 (range 32-93)	

RR will be used for exploratory HR variability analysis

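### SAP 4.6 applies its last-visit-in-window rule to safety data, so by-visit laboratory summaries and C-SSRS can show the later, cleaner record in place of the abnormal one

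*SAP*

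**What the plan says.** **Scope.** SAP 4.6 states: "The reporting windows will be applied to every single data point obtained for analyses regardless of the visit label used to collect the data". Unscheduled visits are named among the labels covered. The title of Table 3 brings safety data in by name: "vitals, physical examination, C-SSRS, ECG, ADAs, hematology, etc".

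**Tie rules.** If several visits map to one window and none is the visit before dopaminergic treatment, the instruction is to "flag the data from the last available visit". If one is that visit, the instruction is "then flag the data from this visit in the analysis". The resulting flag drives by-visit reporting.

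**Repeats.** For unexplained, clinically significant laboratory abnormalities after randomization, Protocol 4.6.1.5 says "the tests should be repeated immediately and followed up until they have returned to the normal range", and it also allows follow-up to end with an adequate explanation. For vital signs, Protocol 4.6.1.3 says: "Any clinically significant abnormal vital sign value should be repeated to ensure accuracy". Protocol 4.6.1.4 makes repeat ECGs optional, to rule out poor lead placement.

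**Safety output.** SAP 4.9.3 plans laboratory summary statistics at each assessment time, and laboratory and blood pressure abnormality incidence by treatment arm. In SAP 4.9.5, the QT/QTc category counts "will be provided by treatment and time-point". SAP 4.9.2 says "C-SSR will be reported by visit", and SAP 4.9.8 adds a C-SSRS shift analysis.

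**The concern.** Choosing the last record in a window is harmless when the timing of extra records has nothing to do with their values. For laboratory tests it does: a second visit in the window often exists because the first result was abnormal, and follow-up may stop once the result is normal. The last record is then partly selected for being normal.

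C-SSRS raises a separate problem. The post-baseline form (Protocol 4.6.1.9) asks about the time since the last visit. A later clean form does not correct an earlier report of ideation; it covers a different period. Flagging only the later form removes a true event from the by-visit display.

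Safety and tolerability are a secondary objective (Protocol 2.2), and SAP Section 1 says the main-body analyses inform the design of the Phase 3 trial. By-visit safety tables that lean toward recovered values are a poor basis for comparing doses.

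**Working it through.** There is no figure in the plan to reproduce. The check is day arithmetic on SAP Table 3, followed by the tie rule.

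**Inputs.** Table 3 scheduled days and windows (SAP 4.6); visit window of +/- 4 days from Week 4 (Protocol Appendix 1); repeat rules (Protocol 4.6.1.3 to 4.6.1.5).

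**Step 1: days left in the window after a scheduled visit.** Days left = window end minus actual visit day.

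| Visit | Scheduled day | Window end | Nominal | Visit 4 days late | Visit 4 days early |
|---|---|---|---|---|---|
| Week 4 | 28 | 41 | 13 | 9 | 17 |
| Week 8 | 56 | 69 | 13 | 9 | 17 |
| Week 24 | 168 | 181 | 13 | 9 | 17 |
| Week 48 | 336 | 349 | 13 | 9 | 17 |

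Every row from Week 4 to Week 48 gives the same result. Week 52 runs to the day before re-randomization. If that takes place on nominal Day 392, the window ends on Day 391 and leaves 391 - 364 = 27 days (23 to 31 with the visit window). The early windows are shorter: 10 - 7 = 3 days after Day 7 and 20 - 14 = 6 days after Day 14.

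**Step 2: does a repeat land in the same window?** There are nine possible visit days (-4 to +4). For Week 4 to Week 48, a repeat d days later stays in the window on this many of them:

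| d (days) | up to 9 | 10 | 13 | 14 | 17 | 18 |
|---|---|---|---|---|---|---|
| Visit days out of 9 | 9 | 8 | 5 | 4 | 1 | 0 |

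A prompt repeat therefore always shares the window.

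**Step 3: apply the tie rule.** Invented example: a laboratory value is 150 at the scheduled visit on Day 56, 70 on Day 60 and 35 on Day 64. All three days lie in the Week 8 window (42 to 69). The flagged Week 8 record is 35; the worst value in the window is 150.

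**Step 4: which outputs use the flag?**
- *Laboratory summaries at each assessment time:* exposed. Haematology is named in Table 3; chemistry and coagulation are covered if the open-ended list is read to include them.
- *C-SSRS by visit:* exposed whenever an earlier form in the window records ideation and a later one does not. The shift analysis does not define its post-baseline value.
- *QT/QTc categories by time-point:* exposed if an abnormal ECG is repeated at a later visit, which is optional.
- *Laboratory and blood pressure abnormality incidence by arm:* the SAP does not say whether flagged or all records count.

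SAP 4.9 contains no worst-value rule for these outputs. Where all samples are meant to count, the SAP says so: ADA status in SAP 4.9.6 is defined on all post-baseline samples.

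**The case against.** **The until-normal rule is narrow.** It covers only unexplained, clinically significant laboratory values and can end with an explanation. Vital signs are repeated for accuracy and ECGs for lead placement. The tie rule chooses between visits, so a confirmatory reading at the same visit is outside it. This stands, and it limits the clear case to laboratory summaries and C-SSRS.

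**The abnormal value is not lost.** A reader might infer that it disappears from the trial. It does not. The Part 1 data cut keeps unscheduled data (SAP 2.6), and listings flag out-of-range values (SAP 4.9.3 to 4.9.5). Clinical significance, which triggers the laboratory repeat, is also a criterion for an adverse event (Protocol 5.3.5.4). This largely stands. However, listings do not compare arms, and SAP 4.9.5 omits specific flagged ECG abnormalities when the overall reading is normal.

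**The main incidence tables may be unaffected.** They are by arm, with no stated visit dimension. This stands as an ambiguity to resolve; it is not evidence of understatement.

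**The rule works both ways.** It can replace a normal scheduled value with a later abnormal one, it keeps a last value that is still abnormal, and the pre-dopaminergic visit takes precedence where present. All true. For laboratory values, though, the repeat is triggered by abnormality, so movement toward normal is the systematic direction.

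**A worst-value rule has its own bias.** It would count readings that the protocol treats as possible error. This is met by excluding documented technical artefacts.

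**Conclusion.** The concern holds for by-visit safety reporting. It is clearest for laboratory summaries, where the protocol generates later records in response to abnormal ones, and for C-SSRS, where successive forms cover different periods. It is possible but weaker for QT/QTc categories. For the by-arm incidence tables the SAP is silent on which records count.

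The size cannot be derived from the documents. If a share r of abnormal values is repeated in-window and a share n of those repeats is normal, the by-visit count falls by r x n. A reader might try r = 0.5 to 0.9 and n = 0.5 to 0.8 and obtain 0.5 x 0.5 = 25% to 0.9 x 0.8 = 72%. Neither input has a source in the documents, repeats are not required for every out-of-range value, and the formula ignores changes in the other direction. That range should not be cited as an estimate.

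A reader might also infer that the relative comparison between doses is distorted. If r and n are the same in every arm, each rate is multiplied by (1 - r x n): absolute differences shrink, but ratios do not change. Distorting the ratio would need r or n to differ by arm, and the documents give no evidence of that.

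The conclusion rests on two assumptions: repeats take place at a separate later visit within the window, and the tie rules are applied to safety data as written.

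**What to change.** In SAP 4.6, limit both tie rules to efficacy endpoints. Then state for safety data:

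- **By-visit continuous summaries:** use the scheduled-visit value.
- **QT/QTc categories; laboratory, vital-sign and ECG abnormality incidence; C-SSRS by visit and shift:** use the worst value in the window, or the worst post-baseline value in Part 1 for tables without a visit dimension. Include unscheduled assessments and exclude readings documented as technical artefacts.
- **By-arm laboratory and blood pressure incidence tables:** say explicitly in SAP 4.9.3 that they follow this rule, which removes the ambiguity over flagged or all records.

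The cost is some SAP wording, one extra derived flag, and abnormality rates that will look slightly higher. No data collection changes.
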